11.4 Expedited Adverse Event Reporting to DAIDS

11.4.1 Adverse Event Reporting to DAIDS

Requirements, definitions and methods for expedited reporting of AEs are outlined in Version 2.0 of the DAIDS EAE Manual, which is available on the RSC website at <http://rsc.tech-res.com/clinical-research-sites/safety-reporting/manual>.

The DAIDS Adverse Events Reporting System (DAERS), an internet-based reporting system, must be used for expedited AE reporting to DAIDS. In the event of system outages or technical difficulties, expedited AEs may be submitted via the DAIDS EAE Form. For questions about DAERS, please contact DAIDS-ES (now part of the NIAID Clinical Research Management System) at [contact]. Site queries may also be sent from within the DAERS application itself.

Sites where DAERS has not been implemented will submit expedited AEs by documenting the information on the current DAIDS EAE Form. This form is available on the RSC website at <http://rsc.tech-res.com/clinical-research-sites/safety-reporting/daids/paper-eae-reporting>. For questions about EAE reporting, please contact the RSC ([contact]).

11.4.2 Reporting Requirements for this Study

The SAE Reporting Category, as defined in Version 2.0 of the DAIDS EAE Manual, will be used for this study.

The study agent for which expedited reporting is required is **isoniazid**. In addition to the EAE Reporting Category identified above, other AEs that must be reported in an expedited manner are all hepatic failures.

11.4.3 Grading Severity of Events

The DAIDS Table for Grading the Severity of Adult and Pediatric Adverse Events (DAIDS AE Grading Table) Version 1.0 - December 2004 (Clarification dated August 2009) is used for this study and is available on the RSC website at <http://rsc.tech-res.com/clinical-research-sites/safety-reporting/daids-grading-tables>.

11.4.4 Expedited AE Reporting Period

The expedited AE reporting period for this study is as per the EAE manual.

After the protocol-defined AE reporting period, unless otherwise noted, only suspected, unexpected serious adverse reactions (SUSARs), as defined in Version 2.0 of the EAE Manual, will be reported to DAIDS if the study staff become aware of the events on a passive basis (from publicly available information).

12.0 PARTICIPANTS

12.1 Institutional Review Board (IRB) Review and Informed Consent

This protocol and the informed consent documents ([Appendix I](#), [Appendix II](#), [Appendix III](#)) and any subsequent modifications will be reviewed and approved by the IRB or EC responsible for oversight of the study. A signed consent form will be obtained from the participant. The consent form will describe the purpose of the study, the procedures to be followed, and the risks and benefits of participation. A copy of the consent form will be given to the participant, and this fact will be documented in the participant's record.

12.2 Participant Confidentiality

All laboratory specimens, evaluation forms, reports, and other records that leave the site will be identified by coded number only to maintain participant confidentiality. All records will be kept locked. All computer entry and networking programs will be done with coded numbers only. Clinical information will not be released without written permission of the participant, except as necessary for monitoring by ACTG, IRB/EC, the NIAID, the OHRP, or **other local, U.S., and international regulatory entities** as part of their duties.

12.3 Study Discontinuation

The study may be discontinued at any time by the ACTG, IRB/EC, the NIAID, the OHRP, or other government agencies as part of their duties to ensure that research participants are protected.

13.0 PUBLICATION OF RESEARCH FINDINGS

Publication of the results of this trial will be governed by ACTG policies.

14.0 BIOHAZARD CONTAINMENT

Transmission of HIV and other blood borne pathogens can occur through contact with contaminated needles, blood, and blood products. Respiratory pathogens such as *Mycobacterium tuberculosis* (MTB) are transmitted by inhalation of droplet nuclei. Appropriate blood, secretion, and respiratory precautions will be employed by all personnel in the collection of clinical samples and the shipping and handling of all clinical samples and isolates for this study, as currently recommended by the Centers for Disease Control and Prevention (CDC) in the United States and the World Health Organization (WHO) internationally.

All protocol specimens will be shipped using packaging that meets requirements specified by the International Air Transport Association Dangerous Goods Regulations for UN 3373, Biological Substance, Category B, and Packing Instruction 650. Culture isolates, if obtained in this study, are to be shipped as specified for UN 2814 Category A Infectious Substances.

Refer to individual carrier guidelines (e.g., Federal Express or Airborne) for specific instructions and to the ACTG/IMPAACT Laboratory Technologists Committee Guidelines for Shipment and Receipt of Category A Infectious Substances and Category B Biological Substances Shipments and Instructions for Overnight Shipments documents at: <http://www.hanc.info/labs/labresources/procedures/Pages/actnShippingDemo.aspx>

Infection control for active TB cases and good laboratory practices for MTB isolation and storage of *Mycobacterium* isolates will be according to ACTG/IMPAACT policies and procedures, CDC/WHO guidance, and local policies and practices to minimize TB transmission.

## 1 Introduction

### 1.1 Purpose

This Primary Statistical Analysis Plan (SAP) describes the primary and secondary outcomes measures of ACTG A5312 that will be included in the primary manuscripts, and which address the primary and secondary objectives of the study. The Primary SAP outlines the general statistical approaches that will be used in the analysis of the study. It has been developed to facilitate discussion of the statistical analysis components among the study team, and to provide agreement between the study team and statisticians regarding the statistical analyses to be performed and presented in the primary statistical analysis report. It also describes the results for the primary and secondary outcome measures that will be posted on ClinicalTrials.gov. Outlines of analyses for the other objectives will be presented in the SAP for Other Objectives. Detailed outlines of tables, figures, and coding descriptions that will be included in the Primary Analysis Report are included in the Analysis Implementation Plan (AIP).

An original component of the EBA study, which would have participants infected with TB with inhA mutations take one of three doses of INH (5, 10, or 15 mg/kg daily) and participants infected with DS-TB take standard-dose INH (5 mg/kg daily), was terminated early by the TB TSG on May 4, 2018. Protocol version 3.0 allows enrollment of participants infected with TB with katG mutations into the EBA part of the study (Step 2) and randomizes them to one of the two treatment groups (15 or 20 mg/kg daily INH). This statistical analysis plan is based on version 3.0. Analysis for the participants infected with TB with katG mutations taking 15 or 20 mg/kg daily will be conducted after approximately 20 eligible participants in this group complete the 7-day treatment period, and data become available.

The two final statistical reports will be used for submission of results to ClinicalTrials.gov. Results are required to be submitted within one year of the primary completion date (PCD), which is the date the last participant with katG mutations is examined for the purposes of data collection for the primary outcome measure.

### 1.2 Key Updates to the SAP

Version	Changes Made	Date finalized
1	Original Version	7/2/2018
1	Protocol amendment review (Version 3.0) by [name] and [name]	3/28/2019
2	Review after LOA #1. Updated the protocol overview to describe the LOA and CMs and personnel changes. The plans for analysis are unchanged.	1/21/2021
3	A new lab, BARC, did culture for TASK participants enrolled in protocol Version 3.0 and reported re-cultured results after additional decontamination. These results were not supposed to be reported (were not reported previously) and will be excluded from analysis. Under protocol Version 3.0 TTP is not done in duplicate for each sample so this has been clarified. Clarified that a separate statistical report will be prepared for participants enrolled under protocol Version 3.0. Added [name] to statistical team.	5/5/2022

## 2 Protocol Overview

### 2.1 Study Design (Protocol Version 3.0)

This is a two-stage, two-step, phase IIa, open-label, randomized clinical trial examining the bactericidal activity (EBA) of (1) isoniazid (INH) at three different doses among patients with drug-resistant tuberculosis (DR-TB) and (2) INH at standard dosing among patients with drug-sensitive TB (DS-TB). In addition, the association between the EBA among patients with DR-TB and pharmacokinetic (PK) parameters, such as area under the curve (AUC)/minimum inhibitory concentration (MIC) of INH, will be examined.

The study will be conducted in 2 stages. Stage 1 will be a pilot for determination of feasibility (accrual and speed) and sample size verification, and Stage 2 will be the main study. During Stage 2, participants with acid fast bacilli (AFB) smear-positive pulmonary TB with a *Mycobacterium tuberculosis* isolate with an inhA mutation, which generally confers low-level INH resistance, will be randomized to receive INH at 5, 10, or 15 mg/kg daily for 7 days (Group 1). Participants with an *M. tuberculosis* isolate with a katG mutation (with or without an inhA mutation), which is associated with high-level resistance, will be randomized 1:1 to receive either INH 15 mg/kg or 20 mg/kg daily for 7 days (Group 3). During Stage 1, participants with *M. tuberculosis* harboring neither inhA nor katG INH resistance mutations (Group 2) will not receive study treatment, but a maximum of 48 in this group will have a sputum sample collected for MIC determination. During Stage 2, Group 2 participants will be enrolled as a positive control group and receive INH at 5 mg/kg daily for 7 days. Among patients receiving study treatment, serial sputum samples, including quantitative cultures and liquid cultures, will be collected daily between pre-entry and Day 7 to determine EBA of the study treatment over the treatment period.

Each stage consists of two steps. The goal of Step 1 is to determine the MIC distribution of *M. tuberculosis* strains among participants with DR-TB or DS-TB. The goal of Step 2 is to examine the treatment effect of INH at different doses among participants with an inhA mutation (in both stages), a katG mutation (in Stage 2 only) or DS-TB (in Stage 2 only). In Step 1, a spot sputum sample will be collected from all eligible participants for acid fast bacilli (AFB) microscopy, for genotypic determination of INH resistance (inhA or katG mutations), and for phenotypic determination of INH MIC. In Step 2, eligible participants will be administered INH daily for 7 days and have serial overnight sputum sampling for estimation of participant-specific EBA (both quantitative and liquid cultures). Intensive PK samples for INH quantification, and blood and saliva samples for NAT2 determination, will also be collected in Step 2.

Participants who are screened for the study, but are not eligible to receive study treatment will be referred without delay for appropriate treatment. Those who are registered or randomized to receive treatment will be referred without delay to appropriate treatment after completing study treatment (no later than Day 10).

**SAMPLE SIZE:** Among participants eligible to participate in Step 1 only, accrual targets are 70, 64, and 64 participants from Groups 1, 2, and 3, respectively. These participants may be enrolled during Stages 1 or 2.

Among participants eligible to enroll in Step 1 and Step 2, accrual targets are as follows:

- Group 1: 48 evaluable participants (16 completing treatment in each dosing cohort) from Stage 1 and Stage 2 combined. During Stage 1, 15 Group 1 participants were enrolled (5 per dosing cohort) as of March 26, 2015. Stage 2 opened and an additional 33 Group 1 participants will be randomized (11 participants added to each cohort, for a total of 16 participants per cohort)
- Group 2: 16 evaluable participants will be followed as a fourth Step 2 cohort, enrolled during Stage 2.
- Group 3: No participants in Group 3 will enter Step 2 during original component (i.e. Protocol Version 2.0). Protocol Version 3.0 will enrolled 20 participants in Group 3 Step 2, randomized 1:1 to either INH 15 mg/kg (n=10) or INH 20 mg/kg (n=10) daily, plus vitamin B6  $\geq$ 25 mg daily for 7 days.

## 2.2 Major Protocol Revisions

Version 2.0 of the study protocol had two Letters of Amendments (LOA). One additional LOA was approved by the TB TSG Steering Committee in September 2016 to improve accrual. Version 3.0 of the protocol was finalized on March 15, 2018. The list below summarizes the main purposes of the LOAs and the changes in Version 2.0 from Version 1.0 and in Version 3.0 from Version 2.0.

- LOA#1 (dated May 4, 2013) – approved on September 17, 2015

The main purpose was to modify the protocol to reflect the decision to conduct A5312 as a non-IND study.

- LOA #2 (dated January 16, 2015) – approved on September 17, 2015

The main purpose was to relax the Step 2 entry criteria to improve recruitment. The changes included, 1) HIV-positive candidates with CD4+ cell count of  $\geq$ 50 cells/mm^3 (instead the original cut off of 200 cells/mm^3) are eligible for the study, and 2) The exclusion of current treatment, or treatment within 30 days prior to entry, with antiretroviral therapy (ART) or expected to initiate ART within 8 days after Step 2 entry has been removed.

- Protocol Version 2.0 (dated August 18, 2015)

The main changes were to increase the target accrual for Groups 1 and 2 during Step 1 (the target accrual for Groups 1 and 2 during Step 2 remains the same), to change the consent forms, to change the inclusion criteria for Group 3 to allow participants who have a katG mutation with or without an inhA mutation to enter study, and update protocol for the completion of Stage 1.

- LOA #1 after Protocol Version 2.0 (dated October 2016) – approved by the TB TSG Steering on September 28, 2016

The main changes were to relax the exclusion criteria on usage of second-line anti-TB drugs and/or antibiotics intended for bacterial treatment prior to Step 1 screening (relaxed Section 4.4.2 and removed Section 4.4.3 of the protocol).

- Protocol Version 3.0 (dated August 21, 2018)

The main purpose of this amendment was to add a treatment cohort for participants with *katG* mutation (Group 3) randomizing them 1:1 to receive either INH 15 mg/kg (n=10) or INH 20 mg/kg (n=10) daily, plus vitamin B6  $\geq$ 25 mg daily for 7 days. Accrual targets were increased for Group 3 to recruit eligible participants.

- LOA #1 for Protocol Version 3.0 (dated August 3, 2020)

On March 18, 2020 the ACTG Network Leadership issued guidance designed to protect the health of ACTG study participants and the ACTG research community and support the best outcomes for our research program. For A5312 this guidance closed recruiting of new study participants but allowed those in screening at that date to be enrolled. The LOA was implemented to reopen the study to screening and accrual.

In addition to the LOAs, five Clarification Memos (CMs) were issued after protocol version 1.0 was released, one CM was issued after protocol version 2.0 was released, and two CMs were issued after protocol version 3.0 was released. The list below summarizes the main purpose of each CM.

- CM#1 (dated July 25, 2013)

The main purpose was to clarify the sample size descriptions in Section 9.4 and 9.6.2.5.

- CM#2 (dated June 27, 2013)

The main purpose was to remove language regarding non-inferiority testing from the protocol.

- CM#3 (dated November 13, 2013)

The main purpose was to remove secondary objective 1.3.5 and the corresponding endpoint (9.2.2.5) and analysis (9.6.2.5).

- CM#4 (dated January 13, 2014)

The main purpose was to clarify that Brooklyn Chest Hospital will participate in Stage 1 of the protocol.

- CM#5 (dated February 4, 2014)

The main purpose was to update the biohazard containment section to include instructions on the transport of *Mycobacterium tuberculosis* material.

- CM#1 on Protocol Version 2.0 (dated February 4, 2014)

The main purpose of this memo was to remove ethambutol (EMB) resistance testing from the study.

- CM #1 on Protocol Version 3.0 (dated December 12, 2019)

The main purpose of this memo was to clarify the sample size under Version 3.0, a total of 40 Group 3 participants, 20 in Step 1 only and 20 in both Step 1 and Step 2. It also clarified that CD4 results from any network-approved lab with IQA certification was acceptable, including that used in inclusion criteria.

- CM #2 on Protocol Version 3.0 (dated February 25, 2020)

This purpose of this memo was to clarify that participants who received 7 days or less of second-line anti-TB drugs in the 14 days prior to Step 1 screening needed to have a washout period of at least 7 days prior to Step 2 pre-entry sputum collection.

This statistical analysis plan is based on protocol version 3.0.

### **2.3 Hypotheses**

1. In the majority of participants infected with TB with inhA mutations, drug concentrations can be achieved that will result in an early bactericidal activity (EBA) measured as the daily fall of  $\log_{10}$  colony-forming unit (CFU)/mL sputum over 7 days (EBA0-7(CFU)) that is at least 50% the EBA0-7(CFU) of standard-dose isoniazid (INH) when given to participants with drug-sensitive TB (DS-TB).
2. High-dose INH will be well-tolerated in a majority of participants.
3. Among participants infected with TB with katG mutations (Group 3), the distribution of minimum inhibitory concentrations (MICs) will be wide, but nevertheless, INH at a dose of 15 or 20 mg/kg daily will have measurable activity.

### **2.4 Primary Objectives**

1. Estimate the 7-day EBA, based on CFU counts, of INH among participants infected with TB with inhA mutations taking one of three doses of INH (5, 10, or 15 mg/kg daily), and participants infected with DS-TB taking standard-dose INH (5 mg/kg daily).
2. Estimate the 7-day EBA, based on time-to-detection (TTD), of INH among participants infected with TB with inhA mutations taking one of three doses of INH (5, 10, or 15 mg/kg), participants infected with TB with katG mutations taking 15 or 20 mg/kg daily, and participants infected with DS-TB taking standard-dose INH (5 mg/kg daily).
3. Determine the association between the area under the curve (AUC)/MIC of INH and the EBA of INH among participants with smear-positive pulmonary TB.
4. Describe the safety and tolerability of doses of 5, 10, and 15 mg/kg of INH administered daily among participants with sputum smear-positive pulmonary TB.

### **2.5 Secondary Objectives**

1. Determine the steady state pharmacokinetics (PK) of INH among participants with sputum smear-positive pulmonary TB taking 5, 10, or 15 mg/kg daily, taking into account INH acetylator status (N-acetyltransferase 2 [NAT2] genotype).
2. Determine and describe the distribution of MICs of *M. tuberculosis* isolates with genotypic evidence of low-level INH resistance (inhA mutations), high-level INH resistance (katG mutations), or neither of these mutations among participants with smear-positive pulmonary TB.

3. Estimate the proportion of participants infected with a TB strain that has an inhA mutation that will achieve a target AUC/MIC that is associated with clinically-relevant reductions in mycobacterial burden defined as at least 50% the EBA0-7 of standard-dose INH when given to participants with DS-TB, by dose.
4. Estimate linear or nonlinear model parameters based on EBA measured separately by CFU counts and time to detection (TTD) for INH among participants infected with TB with inhA mutations taking one of three doses of INH (5, 10, or 15 mg/kg daily), participants infected with TB with katG mutations taking 15 or 20 mg/kg daily (if CFU data are available), and participants infected with DS-TB taking standard-dose INH (5 mg/kg daily).

## 2.6 Exploratory Objectives

1. Evaluate the correlation between EBA0-7 (TTD) and EBA0-7(CFU) among participants with smear-positive pulmonary TB.
2. Evaluate the ability of a new PCR method that uses salivary samples to correctly characterize NAT2 genotype compared to standard NAT2 genotyping methods using blood samples and sequencing methodology.
3. Estimate the prevalence of quinolone, and aminoglycoside resistance among study participants with MDR-TB receiving study treatment.

## 3 Definitions

### 3.1 Analysis Population

Safety population: Safety analyses will be intent-to-treat and include all eligible participants who took at least one dose of study drugs.

Efficacy population: The primary analyses will use a per-protocol approach, limited to participants who provide CFU and TTD data at both study entry and Day 7. For the model based analysis, all randomized participants who had at least one CFU count or TTD will be included.

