1.2 Primary Objectives

- 1.2.1 Estimate the 7-day EBA, based on CFU counts, of INH among participants infected with TB with *inhA* mutations taking one of three doses of INH (5, 10, or 15 mg/kg daily), and participants infected with DS-TB taking standard-dose INH (5 mg/kg daily).
- 1.2.2 Estimate the 7-day EBA, based on TTD, of INH among participants infected with TB with *inhA* mutations taking one of three doses of INH (5, 10, or 15 mg/kg), **participants infected with TB with *katG* mutations taking 15 or 20 mg/kg daily**, and participants infected with DS-TB taking standard-dose INH (5 mg/kg daily).
- 1.2.3 Determine the association between the area under the curve (AUC)/MIC of INH and the EBA of INH among participants with smear-positive pulmonary TB.
- 1.2.4 Describe the safety and tolerability of doses of 5, 10, and 15 mg/kg of INH administered daily among participants with sputum smear-positive pulmonary TB.

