9.2 Endpoints

9.2.1 Primary Endpoints

- 9.2.1.1 Daily decline in \log_{10} CFU per mL sputum from baseline to Day 7 of study treatment, defined as EBA_{0-7} (CFU) = [baseline \log_{10} CFU per mL (mean of the pre-entry visit and entry visit sputum colony counts) – Day 7 \log_{10} CFU per mL]/7 (**Groups 1 and 2**)
- 9.2.1.2 Daily decline in TTD from baseline to Day 7 of study treatment, defined as EBA_{0-7} (TTD) = [baseline TTD (mean of the pre-entry visit and entry visit TTDs) – Day 7 TTD]/7 (**all groups**).
- 9.2.1.3 Daily \log_{10} CFU per mL sputum and TTD from baseline to Day 7 of study treatment; area under the time-concentration curve (AUC) for INH; MIC of *M. tuberculosis* isolates against INH (**Group 1 for CFU and TTD and Group 3 for TTD only**)
- 9.2.1.4 Grade 2 or higher drug-related adverse clinical or laboratory events (**all groups**)

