For Group 1 cohorts, the sample size of 16 is required for a two-sided 95% CI with a precision (half-width) of less than or equal to 0.064 with SDs between 0.060 and 0.120. This means that, for example, if the mean of EBA₀₋₇ (CFU) from the 15 mg/kg of INH for participants with an *inhA* mutation is 0.1 and the SD is 0.12, there is 95% probability that the CI of 0.04 and 0.17 covers the true mean.

Similarly, if the mean of EBA₀₋₇ (CFU) from Group 2 is 0.2 and the SD is 0.12, there is 95% probability that the CI of 0.14 and 0.26 covers the true mean.

This sample size should allow for evaluation of the association between AUC/MIC and EBA₀₋₇, one of the other primary analyses, with high precision, as the data from all experimental dosing cohorts will be pooled for this PK/PD analysis [9, 13, 15, 42].

For Group 3, the sample size of 10 per dosing cohort was selected since the analysis of EBA₀₋₇ (TTP) per dosing cohort will be exploratory. Assuming the SD for Group 3 cohorts will be 6, which is the overall SD of EBA₀₋₁₄ (TTP) from the previous ACTG EBA study (A5307, unpublished), a half-width of a 95% CI is 0.086 with the sample size of 10. This means, for example, if the mean of EBA₀₋₇ (TTP) from a dosing cohort in Group 3 is 13, there is 95% probability that the CI of 9.28 and 16.7 covers the true mean. A possible dosing effect for this group will be examined through visual displays.

Accrual:

During Stage 1, five participants were recruited to each cohort in Group 1. During Stage 2, 11 additional participants will be recruited to each cohort in Group 1, **20 participants in Group 3**, and 16 participants in Group 2 will be recruited. In the final analyses, the data from both stages will be combined. The time to accrual for this study (Stage 1 and 2 combined) is approximately **4 years**.

To maintain desired precision of estimation (primary analyses), participants who discontinue the study prior to the Day 7 evaluations will be replaced. All data from every randomized participant will be stored in the study database, and will be examined for the final analyses.

Participants enrolling to Step 1 only will be considered evaluable if all data that are required are available at screening and/or entry regardless of subsequent known or unknown loss to follow up.

Table 9.4-2: A5312 Accrual Targets

	Resistance Mutation	Participants Completing Step 1 Only ¹	Participants Completing Step 1 and Step 2 ²		Total Participants

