9.6 Analyses

9.6.1 Analyses of Primary Endpoints

9.6.1.1 Descriptive statistics of EBA₀₋₇ (CFU) for each of the cohorts in Groups 1 and 2 will be reported in a table. Box plots and a plot with four CIs will be created.

9.6.1.2 Descriptive statistics of EBA₀₋₇ (TTD) for each of the cohorts will be reported in a table. Box plots and a plot with six CIs will be created.

9.6.1.3 The relationship between the AUC/MIC and the EBA will be evaluated with linear or nonlinear models, adjusting for other covariates, such as baseline log₁₀ CFU per mL. PK/PD modeling will be performed to evaluate the relationship between drug concentrations and rate or magnitude of bacterial decline. The distributions of PK/PD parameters will be examined first and appropriate transformations will be applied if necessary.

9.6.1.4 Grade 2 or higher AEs will be reported in a tabular form by **cohorts**.

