## 4.3 Analyses of Outcomes Measures

### 4.3.1 Primary outcomes

This is a per-protocol analysis in the efficacy population defined in Section 3.1. The primary endpoint is EBA0-7(CFU), which is defined in Section 3.2. Descriptive statistics of EBA0-7(CFU) with N, mean (s.d.), median (IQR), min, and max for each of the cohorts will be reported. Box plot of EBA0-7(CFU) with Q1, median, mean, and Q3 and plot with 95% confidence intervals for the mean EBA0-7(CFU) will be created for each cohort. Note: The analysis for this outcome will be performed for Group 1 and Group 2.

Another primary endpoint is EBA0-7(TTD), which is defined in Section 3.2. Descriptive statistics of EBA0-7(TTD) with N, mean (s.d.), median (IQR), min, and max will be reported by each cohort. Box plot of EBA0-7(TTD) with Q1, median, mean, and Q3 and plot of 95% confidence interval for the mean EBA0-7(TTD) will be created for each cohort.

New grade 2 or higher signs and symptoms, as well as laboratory events will be summarized in a table using SMR. In addition, all new grade 2 or higher signs/ symptoms and laboratory events with relatedness of treatment and most related drugs.

The PK analysis to examine the relationship between the AUC/MIC and the EBA as described in the protocol Section 9.2.1.2 will be provided in a separate PK analysis plan.

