## 5 Report components

Detailed descriptions of the content of each of the following sections are given in the AIP.

1. Recruitment/Accrual
2. Participants and Data Ineligible for Analysis
3. Baseline Characteristics
4. Completeness of Database
5. Study Status
6. Treatment Status
7. Safety
  - Signs and Symptoms and Laboratory Abnormalities
  - Diagnoses
8. Primary Outcomes
9. Secondary Outcomes

Analyses of Group 1 and Group 2 Step 1 and Step 2 and Group 3 Step 1 participants enrolled under Protocol Version 2.0 were complete in 2018. Protocol Version 2.0 did not randomize Group 3 participants to receive any study treatment. Protocol Version 3.0 randomized Group 3 participants who met Step 1 and Step 2 entry criteria to receive 7 days of INH randomized 1:1 to one of two doses: 15 mg/kg or 20 mg/kg. As a result, there will be two separate primary statistical reports for this study:

1. A report Groups 1 and 2 Steps 1 and 2 and Group 3 Step 1 enrolled under Protocol Version 2.0 (complete and dated September 17, 2018)
2. A report covering Group 3 participants enrolled under Protocol version 3.0.

Note: some basic summaries from participants enrolled under Protocol Version 2.0 may also be included in the second report to provide context.

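### SAP 3.1 makes an undefined eligibility test a condition of the safety population, so a dosed participant later found ineligible could be left out of the primary safety table

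*SAP*

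**What the plan says.** The definition in SAP 3.1 is: "Safety analyses will be intent-to-treat and include all eligible participants who took at least one dose of study drugs". It sets two conditions, eligibility and at least one dose, and the SAP nowhere defines the first.

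The same section sets no eligibility condition for the model-based efficacy analysis, in which "all randomized participants who had at least one CFU count or TTD will be included".

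The safety output is described in SAP 4.3.1: "New grade 2 or higher signs and symptoms, as well as laboratory events will be summarized in a table using SMR". Nothing there brings dosed but ineligible participants back in. SAP 5 lists a report component titled "Participants and Data Ineligible for Analysis" and leaves its content to the Analysis Implementation Plan, which is not among the documents.

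In the protocol, safety is primary twice over. Objective 1.2.4 is to "Describe the safety and tolerability of doses of 5, 10, and 15 mg/kg of INH". Endpoint 9.2.1.4, for all groups, is "Grade 2 or higher drug-related adverse clinical or laboratory events". The planned analysis in 9.6.1.4 is that "Grade 2 or higher AEs will be reported in a tabular form by" cohort. Neither 9.2.1.4 nor 9.6.1.4 mentions eligibility.

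**The concern.** A safety analysis should count everyone exposed to the drug. Eligibility errors are sometimes found after dosing, for example when a screening laboratory value is re-read or a history is corrected. Such a participant has been exposed all the same, and any event belongs in the numerator with the person in the denominator. The sentence in SAP 3.1, applied as written, removes both.

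The exclusion need not be unrelated to outcome. Protocol 4.3.4 sets limits on AST/ALT, bilirubin and blood counts. Protocol 4.4.5 excludes known INH allergy, and 4.4.7 excludes Grade 2 or higher neuropathy and epilepsy. Protocol 2.1 describes liver and nervous-system toxicity as known risks of INH. A person dosed despite breaching one of these criteria could plausibly be at higher risk of the events being tabulated.

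What is at stake is the summary of a primary endpoint in small cohorts: 16 per cohort in Groups 1 and 2, and 10 per cohort in Group 3. Group 3 includes 20 mg/kg, the highest dose in the trial. Objective 1.2.4 names only 5, 10 and 15 mg/kg, but endpoint 9.2.1.4 applies to all groups and so covers 20 mg/kg.

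**Working it through.** **Setting the texts side by side**

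| Source | Who is counted | Eligibility condition? |
|---|---|---|
| SAP 3.1, safety | dosed participants who are eligible | yes, undefined |
| SAP 3.1, model-based efficacy | randomized participants with any CFU or TTD result | no |
| Protocol 9.2.1.4, endpoint | all groups | no |
| Protocol 9.6.1.4, analysis | tabulated by cohort | no |

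Three things follow.

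1. On eligibility, the SAP's safety set is narrower than its own model-based efficacy set.
2. The SAP adds a filter to a primary endpoint that the protocol does not have.
3. The intent-to-treat label does not fit. Intent-to-treat conditions on neither dosing nor later eligibility review, and this set conditions on both.

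**Two readings of the word**

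- *Eligible* means meeting all Step 2 criteria on later review. The rule then removes exposed people.
- *Eligible* means having entered Step 2. The word then does nothing, because Step 1-only participants receive no study drug and the one-dose condition already leaves them out.

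Deleting the word corrects the first reading and changes nothing under the second.

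**Size, for illustration**

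The plan states no figure on this point, so there is none to reproduce. The inputs are the cohort sizes (10 in Group 3; 16 in each Group 1 cohort and in Group 2) and an assumed number *k* of dosed participants later found ineligible. The documents do not give *k*. I take 0 to 2 per cohort, and set the number dosed equal to the planned cohort size. Replaced participants who took a dose would make it slightly larger.

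Exact (Clopper-Pearson) 95% limits for *x* events in *n* are:

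- lower = the 0.025 quantile of Beta(*x*, *n* − *x* + 1);
- upper = the 0.975 quantile of Beta(*x* + 1, *n* − *x*);
- for *x* = 0, lower = 0 and upper = 1 − 0.025^(1/*n*).

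For example, 0/9 gives 1 − 0.025^(1/9) = 33.6%.

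With *k* = 0 nothing changes. If the *k* excluded participants had the only events:

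| Dosed | *k* | All dosed | Eligible only |
|---|---|---|---|
| 10 | 1 | 1/10 = 10.0% (0.3% to 44.5%) | 0/9 = 0% (upper 33.6%) |
| 10 | 2 | 2/10 = 20.0% (2.5% to 55.6%) | 0/8 = 0% (upper 36.9%) |
| 16 | 1 | 1/16 = 6.3% (0.2% to 30.2%) | 0/15 = 0% (upper 21.8%) |
| 20 (all Group 3) | 1 | 1/20 = 5.0% (0.1% to 24.9%) | 0/19 = 0% (upper 17.6%) |

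The shift can also go the other way. If the excluded participant had no event and another participant had one, the rate rises from 1/10 = 10.0% to 1/9 = 11.1%.

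**The case against.** The best defence is that *eligible* was never meant as a filter applied after dosing. SAP 1.1 and 2.1 use the word for people who qualify for and enter a step, and the intent-to-treat label sits better with an inclusive intention. This may well be what was meant. It shows that the reading is uncertain, but not that the word should stay: on this reading it is redundant.

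Safety oversight is a second defence, and it stands. Protocol 9.5 has adverse event and toxicity reports reviewed during the study, with any concerns going to the monitoring committee, and 11.4.2 requires expedited reporting of serious events. No eligibility filter is stated for either. Only the final summary could be affected. SAP 4.3.1 plans a table there, with no confidence intervals stated, so the intervals above show scale and do not correspond to a planned output.

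A reader might also infer more than the documents support:

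- *That post-dosing ineligibility is often for a safety reason.* No counts or reasons are given. Several Step 2 criteria (weight range, mutation group, sputum volume, washout) are not of that kind.
- *That the event rate is biased downward.* The direction depends on who is excluded, as the 1/9 example shows.
- *That Protocol 9.4 is contradicted.* It says "All data from every randomized participant will be stored in the study database, and will be examined for the final analyses", directly after the rule on replacing participants who discontinue. It sets no safety denominator, and a separate listing of ineligible participants would satisfy it.
- *That the component in SAP 5 proves exposed people will be dropped.* The heading may refer to other exclusions, such as the contaminated and re-cultured results in SAP 3.2. A dedicated section also suggests disclosure.

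**Conclusion.** The point holds as a defect of definition. SAP 3.1 adds an undefined eligibility condition to the population for a primary safety endpoint, under a label that does not describe it, and without support in Protocol 9.2.1.4 or 9.6.1.4. Followed literally, it can leave exposed participants out of the safety table, and because some entry criteria concern safety, the omission can be related to outcome.

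The actual effect is unknown and may be nil. The illustrated change, from 10.0% to 0% in a cohort of 10 or from 6.3% to 0% in a cohort of 16, rests on two assumptions that the documents do not establish: that one dosed participant was later found ineligible, and that this participant had the cohort's only event. The Analysis Implementation Plan may deal with such participants. The documents do not show that anyone has been or will be left out.

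**What to change.** In SAP 3.1, delete *eligible* and *intent-to-treat* from the safety definition and state:

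> Safety population: all participants who took at least one dose of study drug, regardless of later eligibility findings, analysed by dose received.

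Flag any dosed participant found ineligible in the safety tables, with the criterion breached, so that readers can see the effect of including them. Analysis by dose received should rarely matter, since Protocol 5.5 has doses observed in hospital, but it completes the definition.

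Apply this to the Version 3.0 Group 3 report. SAP 5 dates the Version 2.0 report, which covers the Group 1 and 2 treatment cohorts, September 17, 2018, and describes it as complete. State whether it left out any dosed participant and, if it did, add a footnote so that both reports rest on the same safety set.

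The cost is one sentence in the SAP, a check of the 2018 report and possibly that footnote. No new data are needed.
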